Qualitative and Visual Assessment. The images for the standard ^{99m}Tc -MDP bone scintigraphy and the $[^{18}\text{F}]\text{Fluciclovine}$ -PET/CT will be visually assessed for any artifacts. The images will then be independently scored as described earlier for each imaging modality based on the level of uptake and confidence of tumor presence. The concordance of the agreement will be assessed and compared with the CT determination of metastasis type (lytic, blastic, mixed). Data will then be assessed and tabulated on a lesion by lesion basis for all of the imaging modalities over time as to the presence and the confidence of metastatic prostate cancer. Bland-Altman plots will be prepared.

Semi- and Fully-Quantitative Assessments.

The primary analysis of SUV_{max} and SUV_{mean} will be *t*-tests comparing the osteoblastic and osteolytic lesions. An additional analysis of the primary objective will be one way ANOVA with Tukey's post hoc analysis comparing all four lesion types (osteoblastic, osteolytic, marrow and mixed). As a secondary sensitivity analysis mixed effects models with a fixed effect for lesion type and a random patient effect will also be fit.

Spearman correlation of lesion uptake on ^{99m}Tc -MDP bone scintigraphy and $[^{18}\text{F}]\text{Fluciclovine}$ -PET/CT at baseline and after 3 cycles of Radium 223 will be calculated. The number of lesions identified by ^{99m}Tc -MDP bone scintigraphy alone, $[^{18}\text{F}]\text{Fluciclovine}$ -PET/CT alone, and both ^{99m}Tc -MDP bone scintigraphy and $[^{18}\text{F}]\text{Fluciclovine}$ -PET/CT will be tabulated.

Spearman correlation of lesion uptake on ^{99m}Tc -MDP bone scintigraphy and $[^{18}\text{F}]\text{Fluciclovine}$ -PET/CT at baseline and after 6 cycles will be calculated (6-7 months for those individuals who progressed). The number of lesions identified by ^{99m}Tc -MDP bone scintigraphy alone, $[^{18}\text{F}]\text{Fluciclovine}$ -PET/CT alone, and both ^{99m}Tc -MDP bone scintigraphy and $[^{18}\text{F}]\text{Fluciclovine}$ -PET/CT will be tabulated.

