We focus on separate comparisons of the difference in SUV_{max} and SUV_{mean} in osteolytic vs osteoblastic lesions. Both SUV_{max} and SUV_{mean} are expected to be appreciably higher in osteolytic lesions. The data available for assessment of power is sparse. Oka reported tumor to background (T/BG) ratios of approximately 3 ± 1.0 and 4.5 ± 1.0 (mean \pm SD) for ^{14}C -fluciclovine uptake in osteoblastic and osteolytic lesions respectively in bone metastasis models in mice (Oka et al. 2017). A recent human study by Janssen provides some information that can be used in the current study to determine the sample size (Janssen et al 2017). The study assessed $[^{68}Ga]PSMA-HBED-CC$ uptake in osteolytic, osteoblastic, and bone marrow metastases in prostate cancer patients. It is expected that the $[^{68}Ga]PSMA-HBED-CC$ and $[^{18}F]Fluciclovine$ will behave similarly for the detection of bone metastases depending on the type (blastic, lytic, marrow, mixed). As reported in table 3 of that manuscript, a median SUV_{max} for $[^{68}Ga]PSMA-HBED-CC$ imaging of 10.6 ± 7.1 and 24.0 ± 19.3 in osteoblastic and osteolytic bone metastases in prostate cancer patients with at least one bone metastasis (Janssen et al 2017, The number of osteolytic and osteoblastic lesions in the study were 21/154 (13.6%) and 80/154 (51.9%) respectively, and there were approximately 5 lesions per subject (154 lesions in 30 patients).

Guided by the data in Janssen (Janssen et al., 2017) we assume:

1. 5 lesions per subject. As in Janssen (Janssen et al., 2017) uptake of lesions in the same patient is assumed to be independent.
2. A standard deviation of 14.5 for mean SUV_{max} or SUV_{mean} .
3. The proportion of osteoblastic and osteolytic lesions will be 50% and 13% respectively.
4. The use of separate two sample t - tests at the one sided 0.05 significance level for comparison of SUV_{max} and SUV_{mean} between osteoblastic and osteolytic lesions.

With these assumptions a sample size of 18 evaluable subjects will provide 80% power to detect a difference of 14.7 in mean SUV_{max} or SUV_{mean} between osteolytic and osteoblastic lesions.

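### The primary lytic-blastic t-test is planned on one SD with its variance assumption unstated, and ANOVA/Tukey pools variance; a pooled test would be anti-conservative if spreads differ as in the plan's human source

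*Combined protocol and SAP*

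**What the plan says.** Under Semi- and Fully-Quantitative Assessments, the primary analysis of SUVmax and SUVmean is t-"tests comparing the osteoblastic and osteolytic lesions". An additional analysis is "one way ANOVA with Tukey's post hoc analysis comparing all four lesion types". As a sensitivity analysis, "mixed effects models with a fixed effect for lesion type and a random patient effect will also be fit". Nothing there states the variance assumption of the t-test, the residual structure of the mixed model, or any transformation or rank-based alternative.

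Justification of Sample Size quotes two sources. The human PSMA study gives "10.6 ± 7.1 and 24.0 ± 19.3 in osteoblastic and osteolytic bone metastases"; the text calls these values medians and does not label the ± terms. The mouse fluciclovine study gives tumour-to-background "ratios of approximately 3 ± 1.0 and 4.5 ± 1.0" for blastic and lytic lesions, with the ± terms labelled as SDs. The plan then assumes "A standard deviation of 14.5 for mean" SUVmax or SUVmean and "The proportion of osteoblastic and osteolytic lesions will be 50% and 13% respectively". It adds five independent lesions per subject and separate two-sample t-tests at one-sided 0.05. From these it claims 80% power for a difference of 14.7 with 18 evaluable subjects.

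**The concern.** The human source that supplies the planning figures has a spread 2.7 times larger in lytic than in blastic lesions, and lytic lesions are expected to be about a quarter as numerous. That is the unfavourable pairing for a pooled variance. The large, low-spread group dominates the pooled estimate, while the true uncertainty of the difference comes mostly from the small, high-spread group. A pooled test then understates the standard error and rejects too often.

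The plan had both spreads and combined them into one SD. It then left the choice between a pooled and a Welch test open for its primary comparison. These two tests can have very different error rates on such data, and the choice could be made after the data are seen. The ANOVA/Tukey analysis shares the pooling, so its agreement with a pooled t-test would give no reassurance.

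**Working it through.** **Inputs** (all from Justification of Sample Size)
- Lesions: 18 × 5 = 90. Blastic 0.50 × 90 = 45; lytic 0.13 × 90 = 11.7, taken as 12; other types 90 − 45 − 12 = 33.
- Spreads: 7.1 (blastic) and 19.3 (lytic), treated as SDs. Ratio 19.3/7.1 = 2.72.
- One-sided 0.05, lesions independent, as the plan assumes.

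**The plan's own figures**
- sqrt((7.1² + 19.3²)/2) = 14.54. This reproduces the planning SD of 14.5 as an equal-weight average, and shows that the ± values were read as SDs.
- The 80% power at 14.7 does not reproduce. With a common SD of 14.5, 45 vs 11.7 lesions and one-sided 0.05, power at 14.7 is 92-93%, and 80% power is reached at 11.8-12.0. That mismatch is a separate matter.

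**Pooled against unequal-variance standard error, 45 vs 12 lesions**
- Pooled SD = sqrt((44 × 7.1² + 11 × 19.3²)/55) = 10.72.
- Pooled SE = 10.72 × sqrt(1/45 + 1/12) = 3.48.
- Unequal-variance SE = sqrt(7.1²/45 + 19.3²/12) = 5.67.
- 3.48/5.67 = 0.614, so the pooled SE is 39% too small (39-40% for 11 to 12 lytic lesions).
- Half-width of the 95% interval: 6.98 pooled, 12.38 Welch.
- For comparison, the planning SD gives 14.5 × sqrt(1/45 + 1/12) = 4.71, which is 17% below 5.67.

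**Error rates by simulation** (100,000 to 200,000 normal data sets, equal means, 45 vs 12 lesions)

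| SD ratio lytic/blastic | Pooled, one-sided 5% | Welch, one-sided 5% |
|---|---|---|
| 1.0 | 5% | 5% |
| 1.5 | 9-10% | 5% |
| 2.0 | 13% | 5% |
| 2.72 | about 16% | 5% |

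At 2.72 the pooled two-sided 5% test rejects 23%, so the nominal 95% interval covers 77%. Welch covers 95%.

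**Lognormal alternative.** If SUV is lognormal with SD proportional to level, an exact null makes the SDs equal, and the pooled test rejects about 6%. At the source values, interval coverage is still about 76% pooled, against 90-92% for Welch on the raw scale and 95% for Welch on the log scale.

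**Tukey's lytic-blastic pair.** The plan gives no SDs for marrow and mixed lesions. Assume one SD, s, for the 33 others:
- MSE = (44 × 7.1² + 11 × 19.3² + 31 × s²)/86; SE = sqrt(MSE) × sqrt(1/45 + 1/12).
- s = 7.1: SE 3.11, 45% too small. s = 14.5: SE 3.97, 30%. s = 19.3: SE 4.68, 17%.

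**Planning with Welch and the two SDs** (one-sided 0.05, noncentral t)
- Power at 14.7: 78-79% for 11.7-12 lytic lesions.
- Difference detectable with 80% power: 15.0 (12 lytic) to 15.2 (11.7 lytic).
- If both SDs are really 14.5, Welch power at a difference of 12.0 is about 79%, against 81% pooled.

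**The case against.** The strongest reply is that the plan nowhere calls the t-tests pooled. An analyst who runs Welch has followed the text, and the fault in the primary test disappears. This stands: for the t-test the defect is an unspecified variant. The same holds for the mixed model, whose residual structure is simply not described. It does not hold for ANOVA with Tukey, which in standard form pools.

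A reader might infer that every analysis listed has error bars about 40% too narrow. The documents do not support that. The 39% belongs to a pooled t-test at the human-source spreads. The planning SD gives 17%, and Tukey 17-45% depending on SDs the plan does not give.

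A reader might also take the 2.7-fold ratio as established for this endpoint. It comes from a different tracer and SUVmax only, and the plan calls the available data sparse. Its only fluciclovine figures, in mice, have equal SDs. Against that, those are tumour-to-background ratios rather than SUVs, and the plan itself expects the two tracers to behave alike by lesion type and takes its assumptions from the human study. Ratios of 1.5 to 2.0 would still matter.

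A spread of 67-80% of the centre suggests right skew, and under a lognormal exact null the pooled test is close to its nominal size. So 16% is a conditional figure, not a prediction. Interval coverage would still suffer, although the plan mentions tests and power, not intervals.

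Finally, a difference of 14.71 follows from (1.645 + 0.842) × sqrt(7.1²/45 + 19.3²/11), which might suggest that planning used separate SDs. But 15 subjects, a two-sided test and a common SD of 14.5 also come close to 14.7. The origin cannot be settled from the text, and the written assumption is one SD.

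**Conclusion.** The point holds conditionally. The primary comparison is planned on one SD although the source figures behind it differ 2.7-fold, its t-test variant is unstated, and the ANOVA/Tukey analysis pools variance. If the t-test is pooled and the spreads resemble the human source, the SE is about 39% too small, the one-sided error rate is about 16% instead of 5%, and 95% intervals cover about 77%. This rests on about 45 vs 12 independent lesions, normal data with equal means for the error rate, and ± values that are SDs. The source gives no SUVmean figures, so for SUVmean it further assumes a similar pattern. With equal SDs, or lognormal SUV under an exact null, the error rate is near nominal. The documents do not show that the t-test will be pooled or that fluciclovine SUVs have this spread pattern.

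This should be fixed before analysis. It is not a critical flaw, because the objectives are labelled exploratory and the remedy for the primary test is a short clarification.

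**What to change.** In Semi- and Fully-Quantitative Assessments:
- Name Welch's unequal-variance t-test as the primary lytic-blastic comparison for SUVmax and SUVmean.
- Replace Tukey by Games-Howell for the four-type comparisons.
- Allow lesion-type-specific residual variance in the mixed model if it can be estimated; with about 12 lytic lesions it may be unstable, so state the fallback.
- Optionally add a log-SUV analysis as a sensitivity analysis. It addresses skew but reports a ratio of geometric means rather than the planned SUV difference, so it should not silently replace the primary analysis.

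In Justification of Sample Size, state the two SDs instead of 14.5 and give the Welch detectable difference: about 15.0-15.2 for 80% power with about 12 lytic lesions, under the plan's independence assumption.

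The cost is wording and a software option, with no new data. The detectable difference becomes slightly less favourable than 14.7, and about 2 points of power are lost if the variances are in fact equal.

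### The primary SUV t-tests treat lesions from the same man as independent; no data support this, so their one-sided 5% level is not assured

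*Combined protocol and SAP*

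**What the plan says.** Under Semi- and Fully-Quantitative Assessments, SUVmax and SUVmean are analysed primarily by t-"tests comparing the osteoblastic and osteolytic lesions". A one-way ANOVA with Tukey's "post hoc analysis comparing all four lesion types" is added. Neither has a patient term. The patient appears only in the next sentence: "As a secondary sensitivity analysis mixed effects models with a fixed effect for lesion type and a random patient effect will also be fit". No degrees-of-freedom method is given for that model.

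Under Justification of Sample Size, assumption 1 takes 5 lesions per man and says, with reference to a human study of a different tracer, that "uptake of lesions in the same patient is assumed to be independent". Assumption 4 sets the t-tests "at the one sided 0.05 significance level"; no level is given for the ANOVA. The conclusion is that 18 evaluable men give "80% power to detect a difference of 14.7 in mean" SUVmax or SUVmean. Purpose and Objectives limits the men to at most 5 bone lesions and calls the study exploratory.

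**The concern.** A lesion-level t-test counts every lesion as a separate piece of evidence. On the plan's figures there are 18 × 5 = 90 lesions, of which 13% (about 12) are osteolytic and 50% (45) osteoblastic, all from 18 men. With only about 12 osteolytic lesions, a few men could supply most of them. If those men have high uptake throughout, a difference between men will look like a difference between lesion types, which is exactly the study's hypothesis.

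Two things must both be present for the error rate to rise: correlation of uptake within a man, and grouping of lesion types within men. The document gives a figure for neither. It discloses the independence assumption but does not support it with an intraclass correlation, variance components or a table of types per man. The test concerned is the named primary one and the one used to justify the sample size.

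**Working it through.** **The plan's own power figure.** Inputs from Justification of Sample Size: 12 osteolytic (11.7 before rounding) and 45 osteoblastic lesions, SD 14.5, one-sided 0.05, lesions independent.

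- SE = 14.5 × √(1/12 + 1/45) = 4.71.
- Exact noncentral t: power at 14.7 is 92%, and 80% power is reached at a difference of 11.9 (12.0 with 11.7 lesions).

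The stated 80% at 14.7 therefore does not follow from the stated inputs. It errs on the cautious side, and the point below does not depend on it, but it sets the baseline for power.

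**Error rate of the t-test.** Let ρ be the intraclass correlation of uptake, c the within-man correlation of lesion type, and m the number of lesions per man. When types are drawn with correlation c, the variance of the difference in means is, to a close approximation, the independent-lesion variance multiplied by 1 + (m − 1)cρ. The true one-sided error is then about 1 − Φ(1.645 / √(1 + (m − 1)cρ)). Both ρ and c are assumptions.

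For m = 5 and ρ = 0.4:

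| Grouping | Factor | Formula | Simulated | Simulated, ρ 0.2–0.6 |
|---|---|---|---|---|
| Types at random (c = 0) | 1.0 | 5.0% | 5% | 5% |
| c = 0.25 | 1.4 | 8.2% | 8% | 6–10% |
| c = 0.5 | 1.8 | 11.0% | 11% | 8–13% |
| One type per man (c = 1) | 2.6 | 15.4% | 16% | 11–19% |
| Same mix in every man | below 1 | – | 3% | 2–4% |

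The simulation used 18 men, common SD 14.5, normal patient and lesion effects, 8,000 null trials per cell (Monte Carlo SE 0.2 points near 5%, 0.4 near 16%), and the remaining 37% of lesions split equally between marrow and mixed (assumed). Repeat runs at ρ = 0.4 gave 5–6%, 7–8%, 11–12% and 16–18% for the first four rows. Welch's test was within 0.3 points of the pooled test under the common SD. Trials with osteolytic or osteoblastic lesions in fewer than 2 men were redrawn; this was 3% or less in most groupings but 30% with one type per man.

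**Fewer lesions.** With 1 to 5 lesions per man (assumed uniform), m − 1 is replaced by E(m²)/E(m) − 1 = 11/3 − 1 = 2.67. At ρ = 0.4 the simulated error is 5%, 6%, 9% and 13% for the first four rows (formula 5.0%, 7.2%, 9.2%, 12.6%). Over ρ 0.2–0.6 it is 5%, 6–8%, 7–10% and 10–16%. Inflation is smaller but remains.

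**ANOVA.** At an assumed 5% level, with 5 lesions and ρ = 0.4, the omnibus test rejects in 5%, 12.5%, 22%, 41% and 2% of null trials, in the order of the table.

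**The planned mixed model.** With REML, a random intercept and Kenward-Roger, over ρ 0.2–0.6, error was 4.3–5.8% with 5 lesions and 4.2–5.4% with 1 to 5 lesions (2,500 null trials per cell, SE 0.4 points). A simpler rule, a t reference on men minus 2 degrees of freedom, gave 3.1–5.1% over ρ of 0, 0.3 and 0.5 and c of 0, 0.5 and 1.

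Its power in the same order:

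| Setting | Random | c = 0.25 | c = 0.5 | One type per man | Same mix |
|---|---|---|---|---|---|
| 14.7, 5 lesions, ρ = 0.2 | 92% | 88% | 82% | 74% | 96% |
| 14.7, 5 lesions, ρ = 0.4 | 96% | 92% | 85% | 61% | 99% |
| 12.0, 5 lesions, ρ = 0.4 | 88% | 80% | 71% | 48% | 93% |
| 14.7, 1–5 lesions, ρ = 0.4 | 80% | 76% | 71% | 50% | – |

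**The case against.** The strongest objection concerns the remedy. The mixed model's 5% holds under a common SD, yet the only human SDs in the plan are unequal: "10.6 ± 7.1 and 24.0 ± 19.3 in osteoblastic and osteolytic bone metastases". The planning SD matches their root mean square, √((7.1² + 19.3²)/2) = 14.5. If those SDs held with equal means (14.5 for other types, ρ = 0.4), a model with one residual variance would give 12–16% error. A Welch test that ignores the patient would give 6%, 9%, 10% and 16% across the first four groupings with 5 lesions, which is better except with one type per man. This stands, with three qualifications. Those SDs belong to another tracer, and the fluciclovine figures from mice have equal SDs ("3 ± 1.0 and 4.5 ± 1.0"). The pooled t-test does worst of all under them, at about 17–27%. And type-specific residual variances did not restore 5% in the check made (11–15% in three of four groupings), so no simple variant settles the matter.

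The other objections bear on weight:

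- **The assumption is open and the mixed model is already planned.** True, but if the two analyses disagree, the plan as written lets the t-test govern.
- **The study is exploratory and nothing is decided at the 5% level.** True; this limits the importance.
- **Inflation is conditional.** True. The one-type-per-man figures are a worst case that nothing in the document supports.
- **The cited human study may support independence.** It may, but the document shows nothing from it on this point.

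**Conclusion.** The concern holds as stated: the t-tests' one-sided 5% level is not assured. It is not shown to be inflated. Under a common SD and ρ from 0.2 to 0.6, with 5 lesions per man, the error is 5% if types scatter, 6–13% with moderate grouping (c = 0.25 to 0.5), up to 19% in the worst case, and 2–4% if every man has the same mix. With 1 to 5 lesions per man the moderate-grouping range is 6–10%. The plan cannot know in advance which case applies. The mixed model it already contains holds about 5% in all of these cases, but only under a common SD. The results rest on assumed values of ρ and c and on normal effects. Given the exploratory purpose, this is a cheap improvement that should be made; it does not make the study unworkable.

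**What to change.** 1. Make the planned mixed-effects model the primary analysis of SUVmax and SUVmean: lesion type fixed, patient random, with a named small-sample degrees-of-freedom method such as Kenward-Roger. Take the osteolytic-osteoblastic contrast and the Tukey-adjusted four-type contrasts from it, and state their level and sidedness. Keep the t-tests and ANOVA as descriptive.
2. In Justification of Sample Size, first reconcile 14.7 with its inputs. Then replace the independence assumption with a stated range of intraclass correlation, type grouping and lesions per man, and give the resulting range of power.
3. Report how many men contribute lesions of each type, so that readers can see the grouping.
4. As a sensitivity analysis, check for unequal variances by lesion type, for example with type-specific residual variances or log SUV. Do not claim that this guarantees 5%.

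The cost is SAP wording and a little programming, with no extra patients or scans. Power may fall below the stated 80% if types group strongly (74%, 61% and 53% at 14.7 for ρ of 0.2, 0.4 and 0.6 with 5 lesions and one type per man) or if men have fewer than 5 lesions.
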